4.1.2 Primary Effectiveness Endpoint

The primary effectiveness endpoint for this clinical trial is freedom from AF/AFL/AT episodes of >30 seconds duration that is documented by an ECG (12-lead or TTM) or 24-hour Holter after the initial catheter ablation procedure through 15-months of follow-up (includes a 90-day blanking period followed by a 90-day therapy consolidation period). AF/AFL/AT recurrence during the blanking or therapy consolidation periods will not be considered a treatment failure. One repeat procedure is allowed for ablation of AF/AFL/AT recurrence during the blanking or therapy consolidation periods (≤ 180 days post-initial procedure) without being considered a treatment failure.

AF/AFL/AT recurrence will only be assessed by 12-lead ECG, TTM, and 24-hour Holter monitoring devices for assessment of this primary endpoint so that all subjects are monitored equally with devices of the same sensitivity and specificity. Collected ECG, TTM, and 24-hour Holter data from sites will be evaluated by a physician at a core laboratory for independent and unbiased assessment of AF recurrence for endpoint analysis.

There are multiple situations in which subjects will be considered primary effectiveness endpoint failures:

- If AF/AFL/AT recurrence (>30 second episode) occurs at any time after the therapy consolidation period (>180 days after the initial procedure), or
- If the subject requires a repeat procedure for the treatment of AF after the therapy consolidation period, the subject will be considered an effectiveness endpoint failure regardless of documentation of a >30 second AF/AFL/AT episode, or
- If the subject requires a second repeat procedure at any time after the initial procedure, or
- If the subject requires a new AAD or a previously failed AAD at a dose greater than the highest ineffective historical dose for AF after the therapy consolidation period, or
- If the subject requires a cardioversion (electrical or pharmacological) for the treatment of AF after the therapy consolidation period, or
- If the subject has a continuous atrial arrhythmia throughout a 12-lead ECG recording after the therapy consolidation period indicating arrhythmia recurrence, this will be considered sufficient documentation of recurrence unless there is evidence that the recorded arrhythmia is short-lived and less than 30 seconds.

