4.1.2.1 Rationale for Selection of the Primary Effectiveness Endpoint

4.2 Secondary Endpoints

Type I error among secondary endpoints will be controlled using appropriate statistical methodology as outlined in the Statistical Analysis Plan.

- 1) Proportion of subjects who achieve acute procedural success  for subjects who had the investigational catheter inserted into their vasculature, where acute procedural success is defined as confirmation of entrance block in all pulmonary veins.
- 2) Proportion of subjects off all AADs taken to treat AF/AFL/AT who achieve 15-month success of , defined as freedom from documented AF/AFL/AT recurrence (episodes >30 seconds) during the 9-month period following the blanking and therapy consolidation periods.
- 3) Proportion of subjects who achieve 15-month single procedure success of , defined as freedom from documented AF/AFL/AT recurrence (episodes >30 seconds) during the 9-month period following the blanking and therapy consolidation periods after a single ablation procedure. Any repeat ablation procedure required by the subject at any time will be deemed an effectiveness failure in this analysis.

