
Secondary Endpoints
	
 • Proportion of subjects who achieve acute procedural success of >90% for subjects who had the investigational catheter inserted into their vasculature, where acute procedural success is defined as confirmation of entrance block in all pulmonary veins. • Proportion of subjects off all AADs taken to treat AF/AFL/AT who achieve 15-month success of >40%, defined as freedom from documented AF/AFL/AT recurrence (episodes >30 seconds) during the 9-month period following the blanking and therapy consolidation periods. • Proportion of subjects who achieve 15-month single procedure success of >40%, defined as freedom from documented AF/AFL/AT recurrence (episodes >30 seconds) during the 9-month period following the blanking and therapy consolidation periods after a single ablation procedure. Any repeat ablation procedure required by the subject at any time will be deemed an effectiveness failure in this analysis.

Subject Follow-up
	
 • Baseline, Procedure, Pre-Discharge, 7-days, 3-months, 6-months, 12-months, 15-months 
 • The 7-day, 6-month, and 12-month visits are phone calls to the subject • Baseline, Procedure, Pre-Discharge, 3-month, and 15-month visits are in-person

Inclusion Criteria
	
1) Subject must provide written informed consent prior to any clinical investigation related procedure.

	
 2) Documented symptomatic persistent AF, which is defined as continuous AF sustained beyond 7-days and less than 1-year that is documented by (1) a physician's note AND (2) a 24-hour Holter within 90-days prior to the procedure, showing continuous AF, OR (3) two electrocardiograms (from any form of rhythm monitoring) showing continuous AF, taken at least 7 days apart 3) Refractory or intolerant to at least one Class I or III antiarrhythmic drug (AAD) as evidenced by recurrent symptomatic AF 4) Age 18 years or older 5) Able and willing to comply with all pre-, post-, and follow-up testing and requirements

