#### 1.4.3.2 Chronic success off antiarrhythmic drugs

Proportion of subjects off all AADs taken for the treatment of AF who achieve 15-month success [REDACTED], defined as freedom from documented AF/AFL/AT recurrence (episodes >30 seconds) during the 9-month period following the blanking and therapy consolidation periods.

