#### 2.3.2.2 Chronic Success Off Antiarrhythmic Drugs

This secondary endpoint is chronic success off antiarrhythmic drug; where chronic success is defined as freedom from documented AF/AFL/AT recurrence (episodes >30 seconds) during the 9-month period following the blanking and therapy consolidation periods.

The hypothesis is stated as follows:

[REDACTED]

[REDACTED]

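### As visibly defined, both chronic secondary endpoints can count a subject cardioverted for AF after day 180 as a success, and single-procedure success can do the same for a new or escalated antiarrhythmic drug, although the primary endpoint counts both as failures

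*Protocol*

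**What the plan says.** **Primary endpoint.** CIP 4.1.2 (repeated in Appendix IV and SAP 1.4.2) lists several separate routes to failure. Besides a documented episode after day 180, they include a repeat procedure after day 180, a second repeat at any time, and two rescue events, both counted once day 180 has passed:

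- on drugs: "If the subject requires a new AAD or a previously failed AAD at a dose greater than the highest ineffective historical dose for AF";
- on cardioversion: "If the subject requires a cardioversion (electrical or pharmacological) for the treatment of AF after the therapy consolidation period".

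**Single-procedure success.** CIP 4.2(3), Appendix IV and SAP 1.4.3.3 define it as freedom from documented AF/AFL/AT over 30 seconds "during the 9-month period following the blanking and therapy consolidation periods after a single ablation procedure". One further rule follows: "Any repeat ablation procedure required by the subject at any time will be deemed an effectiveness failure in this analysis". SAP 2.3.2.3 restates the endpoint as freedom from documented recurrence; its visible text does not repeat the ablation rule.

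**Off-drug success.** Appendix IV gives it as "Proportion of subjects off all AADs taken to treat AF/AFL/AT who achieve 15-month success of >40" percent. SAP 1.4.3.2 completes the definition: "defined as freedom from documented AF/AFL/AT recurrence (episodes >30 seconds) during the 9-month period following the blanking and therapy consolidation periods". SAP 2.3.2.2 says the same. Appendix IV also sets the single-procedure goal at more than 40%.

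**Redaction.** The text after the secondary hypotheses is blacked out in CIP 8.2.2.2–8.2.2.3 and SAP 2.3.2.2–2.3.2.3.

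**The concern.** A subject who needs rescue in the evaluation period has not had a durable result from the index treatment, and the primary endpoint scores that subject as a failure. If the secondary endpoints look only at captured rhythm, the same subject can be a success because the rescue worked, or because no qualifying recording was made before it. The success is then credited to the catheter in a test against a fixed goal, in a single-arm trial with no control group to absorb the effect. CIP 4.2 says Type I error is controlled among the secondary endpoints, so these are formal claims and not only descriptive results.

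**Working it through.** **1. Do the primary failure rules carry over?** Four places in the documents bear on this.

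- CIP 4.1.2 introduces its list as failures of the primary effectiveness endpoint.
- The single-procedure endpoint has its own sentence on repeat ablation. That sentence would be largely redundant if the primary list were inherited, and it is silent on drugs and cardioversion.
- CIP 6.2.2 says AAD users without documented recurrence are not effectiveness failures. Its exception for a new or escalated AAD is worded for the primary endpoint only.
- CIP 4.3 item 2 and SAP 1.4.4 item 2 define success by rhythm and then add absence of AAD escalation as a further condition. Success alone therefore does not exclude escalation. That drug-adjusted measure is descriptive and is not tested.

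**2. Event by endpoint, on the visible text.**

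| Primary failure event | Single-procedure success | Off-drug success |
|---|---|---|
| Cardioversion for AF after day 180 | not a failure | not a failure |
| New or escalated AAD after day 180 | not a failure | excluded while on the drug; not addressed if later stopped |
| Late repeat or third ablation | failure (express rule) | not in the definition; CIP 6.6.1 may cover it |
| Continuous arrhythmia on 12-lead ECG | plausibly covered as documentation | plausibly covered as documentation |

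**3. Worked cases.**

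- A subject starts a new AAD on day 200 for symptoms, no episode over 30 seconds is captured, and the drug holds the rhythm to month 15. This is a primary failure and a single-procedure success.
- A subject is cardioverted on day 250 at an outside hospital with no recording that qualifies as documentation. This is a primary failure. It can be a single-procedure success and, if the subject is off AADs, an off-drug success. The case assumes that the primary endpoint's limit on recording methods also applies to the secondary endpoints, which the documents do not state.

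**4. Can rescue occur without a captured episode?** After day 180 the schedule in CIP 6.6 and Table 4 has 24-hour Holters at 6, 12 and 15 months, monthly and symptom-triggered transtelephonic recordings, and one scheduled 12-lead ECG at 15 months. At an unscheduled visit a 12-lead is recorded only if one was done (CIP 6.6.2). Monitoring is intermittent, so it can occur. The documents give no frequency.

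**5. Size per subject.** Inputs are 224 subjects and 20% attrition (CIP, visible fragment of the sample size section).

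- 224 × (1 − 0.20) = 179.2, so about 179 evaluable. In reverse, 179 / 0.80 = 223.75, which rounds up to the plan's 224.
- Shift per reclassified subject: 1/224 = 0.45 points; 1/179 = 0.56 points.

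**6. Illustration of the effect on the test.** Assumptions: 179 evaluable subjects, an exact one-sided binomial test against 40%, and alpha of 0.025 or 0.05 (the actual alpha is redacted). The smallest passing count is 86/179 = 48.0% at 0.025, or 83/179 = 46.4% at 0.05. Suppose the true rate with every primary failure counted is exactly 40%, and the narrower definition adds d points. The chance of passing is then:

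| d (points) | alpha 0.025 | alpha 0.05 |
|---|---|---|
| 0 | 1.8% | 4.9% |
| 1 | 3.3% | 8.4% |
| 2 | 6.0% | 13.4% |
| 3 | 9.9% | 20.2% |
| 5 | 22.8% | 38.4% |

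Three points is 0.03 × 179 ≈ 5 subjects; five points is 0.05 × 179 ≈ 9. These values of d are assumptions.

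**The case against.** The best counter-case is that the narrower definition is deliberate. SAP Appendix D gives the visible reason for the single-procedure endpoint as catching recurrence, including asymptomatic recurrence. A rhythm-only secondary beside a composite primary fits that purpose, and CIP 6.2.2 ties the AAD rule to the primary as if by choice. Nothing visible says the secondaries were meant to be stricter than the primary. This stands as an explanation. It does not remove the effect on a tested rate, and a rhythm-only figure can be reported descriptively.

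The redactions also count: the blacked-out text may contain the missing rules. The claim therefore extends only to what the visible definitions say. Those definitions are complete sentences in CIP 4.2, Appendix IV and the SAP endpoint section, and the rule belongs there.

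The affected subjects must also escape both symptom-triggered and scheduled recording, so they may be few.

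A reader might infer more than the documents support:

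- *Single-procedure success ignores repeat ablation.* It does not; any repeat is a failure.
- *Off-drug success credits rescue drugs in general.* It requires being off all AADs. Only a rescue drug later stopped is open, because the visible text does not say when off-drug status is assessed.
- *Off-drug success clearly ignores late or third ablations.* CIP 6.6.1 calls these effectiveness endpoint failures without limiting that to the primary.
- *The 12-lead rule is dropped.* It states what suffices to document a recurrence, and both secondaries rest on documented recurrence.

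**Conclusion.** The point holds in limited form. On the visible text, cardioversion for AF after day 180 is not a failure for either chronic secondary endpoint, and a new or escalated AAD after day 180 is not one for single-procedure success. For off-drug success, a late or third ablation is not in the definition, and a rescue AAD later stopped is not addressed. With no captured episode, such a subject is a primary failure and can be a secondary success.

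The effect on the tested rates is upward, by 0.45 to 0.56 points per subject. The total cannot be computed because the number of such subjects is unknown; the pass probabilities shown are conditional on assumed values.

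A reader might also infer that the primary and single-procedure results become uninterpretable side by side. That is not supported. The single-procedure rate would exceed the primary rate only if subjects reclassified as successes outnumbered primary successes who had the one permitted early repeat ablation, and nothing in the documents indicates that.

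**What to change.** In CIP 4.2(2)–(3), Appendix IV, SAP 1.4.3.2–1.4.3.3 and SAP 2.3.2.2–2.3.2.3, add one sentence: a subject who meets any primary effectiveness failure criterion in CIP 4.1.2 is also a failure for this endpoint. Keep the existing rule that any repeat ablation fails single-procedure success, and repeat it in SAP 2.3.2.3. For off-drug success, state when off-AAD status is assessed. If the rhythm-only rate is of interest, report it descriptively. If the redacted text already contains these rules, bring the endpoint definitions into line with it.

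The cost is a text change to the CIP and SAP. No new data are needed, because the events must already be collected for the primary endpoint. The downside is slightly less favourable secondary success rates.

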## Statistical Analysis Plan

### 1.0 SYNOPSIS OF STUDY DESIGN

#### 1.1 Purpose of the Statistical Analysis Plan

This statistical analysis plan (SAP) is intended to provide a detailed and comprehensive description of the planned methodology and analysis to be used for the CRD 901 PERSIST-END clinical investigation.

#### 1.2 Clinical Investigation Objectives

The objective of this clinical trial is to demonstrate that ablation with the TactiCath™ Contact Force Ablation Catheter, Sensor Enabled™ (TactiCath SE) is safe and effective for the treatment of drug refractory, symptomatic persistent atrial fibrillation (AF) when following standard electrophysiology mapping and radiofrequency (RF) ablation procedures.

#### 1.3 Clinical Investigation Design

This is a prospective, single-arm, multi-center IDE clinical trial to evaluate the safety and effectiveness of ablation with the TactiCath SE catheter for the treatment of drug refractory, symptomatic persistent AF compared to a predetermined performance goal. A total of 224 subjects will be enrolled at up to 25 investigational sites worldwide.

Subjects will be followed for 15 months after their initial ablation procedure. The 15-month follow-up includes a 90-day blanking period and 90-day therapy consolidation period followed by a 9-month follow-up period. The primary endpoints will be evaluated when all subjects have completed their 15-month follow-up visit.

The pre-market approval (PMA) clinical report will be prepared after the last subject has completed their final follow-up visit or has passed the end of their final follow-up visit window.

#### 1.4 Endpoints

##### 1.4.1 Primary Safety Endpoint(s)

The primary safety endpoint is the rate of device and/or procedure-related serious adverse events with onset within 7-days of any ablation procedure that uses the TactiCath SE catheter (initial or repeat procedure performed  $\leq 180$  days of initial procedure) that are defined below:

- Atrioesophageal fistula\*
- Cardiac tamponade/perforation\*
- Death
- Heart block
- Myocardial infarction (MI)
- Pericarditis^
- Phrenic nerve injury resulting in diaphragmatic paralysis
- Pneumothorax
- Pulmonary edema (respiratory insufficiency)
- Pulmonary vein stenosis\*

## Statistical Analysis Plan

- Stroke/cerebrovascular accident (CVA)
- Thromboembolism
- Transient ischemic attack
- Vascular access complications (including major bleeding events#)

\* Atrioesophageal fistula, cardiac tamponade/perforation and pulmonary vein stenosis will be evaluated through 15-months.

^ Pericarditis is a common occurrence for almost all procedures and will only be considered a primary safety endpoint event if the pericarditis pleuritic symptoms last longer than 7-days and/or requires hospitalization of greater than 24 hours for reasons other than for observational purposes only.

# Bleeding is a major complication of AF ablation if it requires and/or is treated with transfusion or results in a 20% or greater fall in hematocrit.

Serious AF/atrial flutter (AFL)/atrial tachycardia (AT) recurrences without coexisting conditions (e.g. thromboembolism, worsening heart failure, etc.) will be counted as effectiveness failures but will not count against the primary safety endpoint.

### 1.4.2 Primary Effectiveness Endpoint(s)

The primary effectiveness endpoint for this clinical trial is freedom from AF/AFL/AT episodes of >30 seconds duration that is documented by an ECG (12-lead or TTM) or 24-hour Holter after the initial catheter ablation procedure through 15-months of follow-up (includes a 90-day blanking period followed by a 90-day therapy consolidation period). AF/AFL/AT recurrence during the blanking or therapy consolidation periods will not be considered a treatment failure. One repeat procedure is allowed for ablation of AF/AFL/AT recurrence during the blanking or therapy consolidation period ( $\leq 180$  days post-initial procedure) without being considered a treatment failure.

AF/AFL/AT recurrence will only be assessed by 12-lead ECG, TTM, and 24-hour Holter monitoring devices for assessment of this primary endpoint so that all subjects are monitored equally with devices of the same sensitivity and specificity. Collected ECG, TTM, and 24-hour Holter data from sites will be evaluated by a physician at a core laboratory for independent and unbiased assessment of AF recurrence for endpoint analysis.

There are multiple situations in which subjects will be considered primary effectiveness endpoint failures:

- If AF/AFL/AT recurrence (>30 second episode) occurs at any time after the therapy consolidation period (>180 days after the initial procedure), or
- If the subject requires a repeat procedure for the treatment of AF after the therapy consolidation period, the subject will be considered an effectiveness endpoint failure regardless of documentation of a >30 second AF/AFL/AT episode, or
- If the subject requires a second repeat procedure at any time after the initial procedure, or
- If the subject requires a new AAD or a previously failed AAD at a dose greater than the highest ineffective historical dose for AF after the therapy consolidation period, or
- If the subject requires a cardioversion (electrical or pharmacological) for the treatment of AF after the therapy consolidation period, or
- If the subject has a continuous atrial arrhythmia throughout a 12-lead ECG recording after the therapy consolidation period to indicating arrhythmia recurrence, this will be considered sufficient documentation of recurrence unless there is evidence that the recorded arrhythmia is short-lived and less than 30 seconds.

As cavotricuspid isthmus-dependent atrial flutter is easily treated with cavotricuspid isthmus ablation and is not an iatrogenic arrhythmia following a left atrial ablation procedure for AF, occurrence of cavotricuspid isthmus-dependent atrial flutter confirmed by entrainment maneuvers that occurs at any time during the follow-up period

## Statistical Analysis Plan

and is ablated, will not be considered a primary effectiveness endpoint failure.

### 1.4.3 Secondary Endpoint(s)

#### 1.4.3.1 Achievement of acute procedural success

Proportion of subjects who achieve acute procedural success [REDACTED] for subjects who had the investigational catheter inserted into their vasculature, where acute procedural success is defined as confirmation of entrance block in all pulmonary veins.

#### 1.4.3.2 Chronic success off antiarrhythmic drugs

Proportion of subjects off all AADs taken for the treatment of AF who achieve 15-month success [REDACTED], defined as freedom from documented AF/AFL/AT recurrence (episodes >30 seconds) during the 9-month period following the blanking and therapy consolidation periods.

#### 1.4.3.3 15-month single procedure success – freedom from asymptomatic and symptomatic AF/AFL/AT recurrence

Proportion of subjects who achieve 15-month single procedure success [REDACTED], defined as freedom from documented AF/AFL/AT (episodes >30 seconds) during the 9-month period following the blanking and therapy consolidation periods after a single ablation procedure. Any repeat ablation procedure required by the subject at any time will be deemed an effectiveness failure in this analysis.

### 1.4.4 Additional Data

Additional data to be collected in this clinical investigation are described and will be reported using summary statistics, including but not limit to the following:

- 1) Procedure- and/or ablation catheter-related adverse events throughout the 15-month follow-up period
- 2) Success (defined as freedom from >30 second documented episodes of AF/AFL/AT recurrence) without Class I or III AAD dose increase from the historic maximum ineffective dose (prior to the ablation procedure) or initiation of a new Class I or III AAD for arrhythmia recurrence after the blanking and therapy consolidation periods.
- 3) Proportion of subjects who achieve 15-month symptomatic single procedure success (defined as freedom from >30 second documented symptomatic episodes of AF/AFL/AT recurrence) after the blanking and therapy consolidation periods.
- 4) Cardiovascular-related health care utilization through 15-months after the initial procedure.
- 5) Procedure data, including but not limited to, ablation data, mapping data, and usage of Automark.
- 6) Proportion of cases achieving  $\geq 90\%$  lesions with  $\geq 10g$  of contact force.
- 7) Evaluation of procedure data to determine target lesion index (LSI) value(s) as assessed by AF/AFL/AT recurrence.
- 8) Changes in EQ-5D-5L and AFEQT scores from baseline to follow up at 3, 6, 12, and 15-months after the initial procedure.
- 9)

